2. BACKGROUND

- 2.1. **Malignant Gliomas:** Malignant gliomas are among the most virulent tumors. High-grade gliomas are divided into Grade III gliomas (including anaplastic astrocytoma, anaplastic oligodendrogloma, and anaplastic oligoastrocytomas) and Grade IV which are termed Glioblastoma Multiforme (GBM). GBM is the most common primary brain tumor and the most aggressive. The five-year survival for GBM is dismal and multiple treatment modalities have been unsuccessful. Stupp et alⁱ defined the standard of care in 2005 with the combination of temozolomide and radiation therapy increasing the 2-year survival with this regimen from 10.3% in the radiation only arm to 26.5% in the combination arm. This has defined the standard of care but still just 3% of patients are surviving at 5 years.
- 2.2. **Ketone metabolism:** Gliomas cells in contrast to normal glial cells rely on glucose and glycolysis for division and survival. Normal glial cells can survive on ketones alone but it is hypothesized that glioma cells cannot utilize ketone bodies as energy substrate.ⁱⁱ The Akt/phosphoinositide 3-kinase (PI3K)/mammalian target of rapamycin (mTOR) (AKT/PIK3/MTOR) pathway has been implicated in the inhibition of cell death and is activated by glucose and glycolysis. This pathway is found in many gliomas.ⁱⁱⁱ Ketone metabolism has been used to control childhood epilepsy for many years and this is thought to be through inhibition of the AKT/PIK3/MTOR pathway and other mechanisms.^{iv} Abdelwahab implanted mice

with malignant glioma cells to study the effect of ketosis on survival and glioma control. The mice had a modest increase in survival with ketone metabolism as compared to control mice not on the ketogenic diet. However, when radiation was added to the treatment (with or without the ketogenic diet) there was a significant increase in survival so much so that tumor cells could no longer be detected in the ketogenic arm. The mice were switched to a non-ketogenic diet after 101 days and no signs of recurrence were seen for over 200 days in the radiation and ketogenic diet arm.^v

Ketone bodies may act as a radiation sensitizing agent and this would explain the significantly increased survival in the mice that received the ketogenic diet with radiation as compared to the mice that received the ketogenic diet alone.

Caloric restriction is also important in glioma control. Seyfried et al. injected mice with CT-2A glioma cells. Mice were placed on a caloric restriction diet or a regular diet with and without ketone body supplementation. The ketone supplemented diet alone did not predict increased overall survival. Caloric restriction was an important contributor to decrease in tumor size and increase in overall survival. Caloric restriction inhibits the insulin growth factor-1 pathway (IGF-1) pathway and therefore inhibits tumor growth. Combined caloric restriction and serum ketosis achieved greater tumor control and mouse survival.^{vi} Seyfried, however, conducted this study without radiation. *From this data, our hypothesis is that both decreased glucose and ketosis in conjunction with radiation are necessary to produce tumor reduction in gliomas.*

There is limited data in humans with ketogenic diets and cancer but because of the preliminary data in mice of the effect of ketones and radiation on gliomas and the retrospective data in humans with glioblastoma that hyperglycemia decreases survival,^{vii} there are multiple on-going trials. Champ et al. retrospectively studied 6 patients with glioblastoma on the ketogenic diet. The six patients had lower blood glucose and higher ketone levels than their counterparts and tolerated the diet well.^{viii} Nebeling et al studied two pediatric patients with anaplastic astrocytoma (high grade gliomas) and found that the diet was tolerated and safe. The two patients had significant decreases in glucose, increases in ketone levels and decreases in glucose

uptake on FDG-PET.^{ix} Again given the retrospective nature of these studies, it is difficult to draw any unbiased conclusions from this data.

2.3. **Modified Atkins Diet (MAD):** The form of the KD used in pediatric epilepsy is composed of a 4:1, fat to carbohydrate plus protein ratio. However, the modified Atkins diet (MAD) (<20 grams of carbohydrates per day) produces ketosis and has been used in the treatment of adults with epilepsy with the same efficacy. Notably, there is better compliance with the MAD than with the traditional KD. Many studies have also shown improved tolerability the MAD in the adult population as compared to the traditional ketogenic diet.^x

2.4. **Cognitive Outcomes:** We have shown in older adults with Mild Cognitive Impairment (MCI), a risk condition for Alzheimer's disease, that dietary ketosis achieved through carbohydrate restriction, improves memory performance (Fig 1).

[figure not shown]

Figure 1.
Pre- and
post-intervention

memory performances for low and high carbohydrate participants with MCI as measured by the Verbal Paired Associate Learning Test, $F(1,20) = 6.45, p = 0.01$, Cohen's $f = 0.26$ (Krikorian et al. 2012).

In addition to these improvements in memory performance in older adults, we observed preliminary indications that dietary ketosis is associated with enhanced neuronal integrity and increased bioenergetic function in pre- and post-dietary intervention studies using proton magnetic resonance imaging (^1H MRS) in older adults with MCI (Krikorian et al. 2014; Fig 2).

[figure not shown]

Figure 2. Effect and trends indicating increased myo-inositol, N-acetyl-aspartate, and creatine + phosphocreatine in older adults with MCI following six weeks of nutritional ketosis induced by carbohydrate restriction.

In addition, our colleague, [name] at the University of Kentucky, has developed a method to assess platelet mitochondrial function and *demonstrated significant changes in mitochondrial function in blood platelets preceding changes in brain mitochondrial function* in a trichloroethylene (TCE) rodent model.

Mitochondrial respiratory capacity in platelets isolated from animals (n=3-5/group) that had been exposed to TCE (1000 mg/kg, oral gavage daily) was assessed for different periods (1 hour to 7 days). Chronic TCE exposure induces a Parkinsonian disease state. (Fig 3). In addition, wild type (WT) mice and mice overexpressing human wild type alpha synuclein (aSyn), a pathological factor in Parkinson's disease neuropathology, under the Thy1 promoter (Thy1-aSyn) were placed on a ketogenic or control diet. Mitochondrial respiration was measured in mitochondria isolated from the striatum from mice fed a ketogenic or standard diet for 28 days. Thy1-aSyn mice fed a standard diet displayed significantly diminished mitochondrial efficiency compared to WT mice on the standard diet and Thy1-aSyn mice fed the ketogenic diet displayed mitochondrial efficiency rates similar to WT mice (Fig 4).

[figure not shown]

Figure 3. TCE exposure reduces mitochondrial function in a progressive manner. In contrast, measurable change in brain mitochondria requires two weeks of chronic exposure. Thus, the peripheral measure may function as an early marker brain mitochondrial dysfunction in animal and human PD. Bars = means \pm SD

[figure not shown]
[figure not shown]

Figure 4: Mitochondria were isolated from striatum and oxygen consumption rate (OCR) was measured in WT and Thy1-aSyn mice at 3m of age and 28 days on a ketogenic or standard diet. Mitochondrial oxygen consumption is significantly reduced in Thy1-aSyn mice fed a standard diet but not in Thy1-aSyn mice fed a ketogenic diet. N=3 in each condition, * Represents $p < 0.05$, ANOVA

Very recently, we obtained data demonstrating enhanced peripheral platelet mitochondrial efficiency through nutritional ketosis in overweight, middle-aged individuals with memory complaints, factors that confer greater risk for late-life dementia. Figure 5 shows preliminary data from four participants randomized to either the higher carbohydrate or

lower carbohydrate ketogenic protocols. Platelet assays from participants randomized to the low carbohydrate arm exhibited enhanced state III respiration and uncoupling.

These preliminary studies demonstrate our ability to administer the carbohydrate-restricted, ketogenic diet with research participants and the efficacy of this intervention with respect to neurocognitive function. Further, in collaboration with [name], we have shown in animal and, more recently in humans, that this intervention influences mitochondrial function favorably.

3. STUDY DESIGN

- 3.1. This is a single arm feasibility study.
- 3.2. Study Diet: Patients will be screened for study eligibility and written informed consent will be obtained prior to enrollment. Patients will meet with the registered dietitian (RD) one to four weeks prior to initiation of concurrent radiation and chemotherapy. At that visit, the RD will provide education on all aspects of MAD including meal planning and daily food diary completion (Appendix II). The diet will begin approximately 7 days prior to the initiation of concurrent radiation and chemotherapy and the patient will continue the study diet until the first post-radiation MRI, a time period of approximately 10 weeks. We will obtain blood to assess serum BHB, fasting insulin and glucose, and other chemistries as well as body weight weekly, according to the standard of care, while on chemotherapy and radiation therapy. Participants will receive weekly phone calls from the RD to address any questions or concerns the patient may have regarding the MAD and daily food diary. A food diary (Appendix II) will be used to assess adherence during the 10-week period. All macronutrient intake from food diaries will be entered by study agent into nutrient analysis software. This macronutrient breakdown will be utilized to identify potential problematic macronutrient intake which may be preventing patient from achieving ketosis. This is available online as well.
 - 3.2.1. Temozolomide and radiation will be given according to the standard protocol described by Stupp et al.ⁱ Patients will receive 75 mg/m² of temozolomide concurrent with radiation therapy at standard dose. The dose of radiation and/or chemotherapy and/or steroid may be modified by the attending physician based on clinical indications.
 - 3.2.2. Correlative platelet mitochondrial studies will be drawn on the pre-treatment visit #2, the post-treatment visit #1 and the post-treatment visit #2. Patients are already having blood drawn at these visits as standard of care. This sample will be transported within 6 hours to the laboratory **[name] at Cincinnati Children's Hospital Medical Center** for assessment of mitochondrial respiration in the platelets.
 - 3.2.3. QOL studies will be done at the pre-treatment visit #2, pre-treatment visit #3, weekly during chemotherapy and radiation, at the post-treatment visit #1 and then at post-treatment visit #2
 - 3.2.4. Neurocognitive testing will be performed at the pre-treatment visit #2, at the post-treatment visit #1 and then at post-treatment visit #2
- 3.3. **Number of Participants:** Thirty evaluable patients will be enrolled. Because this is a feasibility study, ECOG performance status and MGMT methylation which are both predictors of survival will be recorded but not used for stratification.

4. PATIENT SELECTION

4.1. Inclusion Criteria

- 4.1.1. Patients must have a histologically confirmed primary malignant glioma (Grade III (1p/19q intact) or Grade IV tumor). Patients can have a radiographically confirmed diagnosis if biopsy is not possible, but this must be approved by the primary investigator.

- 4.1.2. No uncontrolled infection or other active malignancy or chronic systemic immune therapy.
- 4.1.3. Age ≥ 18 years.
- 4.1.4. ECOG performance status ≤ 3 (see Appendix A).
- 4.1.5. Life expectancy $>$ three months.
- 4.1.6. Ability to understand and willingness to sign a written informed consent document.
- 4.1.7. Patients can be on an investigational study but will not be eligible if the investigational drug is given during the intervention
- 4.1.8. Physician must have the intent to treat with the Stupp Protocol.
(<http://www.nejm.org/doi/full/10.1056/NEJMoa043330>)
- 4.1.9. Patient must be on steroid dose of dexamethasone ≤ 8 mg at study entry.
- 4.1.10. Adequate renal function, defined as follows: Serum creatinine \leq institutional ULN within 14 days prior to registration. Creatinine clearance (CC) ≥ 60 ml/min within 14 days prior to registration determined by 24- hour collection or estimated by Cockcroft-Gault formula: CC_{Cr} male = [(140 – age) x (wt in kg)] [(Serum Cr mg/dl) x (72)]; CC_{Cr} female = 0.85 x (CrCl male)
- 4.1.11. Adequate hepatic function defined as follows: Total bilirubin $< 2 \times$ institutional ULN within 14 days prior to registration; AST or ALT $< 3 \times$ institutional ULN within 14 days prior to registration.

4.2. Exclusion Criteria: The presence of any of the following will exclude a patient from study enrollment.

- 4.2.1. Patients who are pregnant
- 4.2.2. Patients with a genetic disorder of fat metabolism.
- 4.2.3. Patients with IDDM or Type 2 diabetes diagnosed with a hemoglobin A1C > 6.4
- 4.2.4. Patients who are allergic to dairy or lactose intolerance
- 4.2.5. Patients with known inborn errors of metabolism of primary carnitine deficiency, carnitine palmitoyltransferase I or II deficiency, carnitine translocase deficiency, beta-oxidation defects, pyruvate carboxylase deficiency and porphyria.
- 4.2.6. Patients with pancreatic insufficiency or history of pancreatitis within last 5 years
- 4.2.7. Patients with gallbladder dysfunction or disease
- 4.2.8. Decompensated congestive heart failure

4.3. Inclusion of Women and Minorities: Men, women and members of all races and ethnic groups are eligible for this trial.

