 - ii. Complete metabolic panel, fasting serum glucose and insulin levels
 - iii. Vital signs, body weight, waist circumference
 - iv. Quality of Life (FACT-Br) survey (See Appendix I)
 - c. Weekly telephone contact with RD to address diet related concerns
6. Radiation and temozolomide treatment terminated
 - a. Continued MAD until MRI (Day 43-70)
7. MRI and post-treatment visit #1 (approximately Day 70)
 - a. Meet with RD

- i. If patient wishes to discontinue research diet, RD will instruct patient on 3-day titration back to pre-study carbohydrate intake levels.
- ii. If patient wishes to continue longer term discuss supplement use to prevent nutritional deficiencies from long-term diet.
- b. Meet with attending physician
 - i. Review MRI findings
 - ii. Review post-intervention maintenance chemotherapy
 - iii. Laboratory Correlatives
 - i. Lipid profile, complete metabolic panel, complete blood count with differential (CBC with diff), and hemoglobin A1C
 - ii. Serum BHB
 - iii. Fasting serum glucose and insulin
 - iv. Vital signs, body weight, waist circumference
 - v. Platelet mitochondrial Labs
 - iv. Adverse Events
 - v. Performance Status
 - vi. Quality of life (FACT-Br) survey (See Appendix 1)
 - vii. Neurocognitive testing (See Appendix VI)
- 8. MRI and Ppost-treatment visit #2 (approximately day 126-154 after post-treatment MRI)
 - a. Meet with attending physician
 - i. Review MRI findings
 - ii. Review post-intervention maintenance chemotherapy
 - iii. Laboratory Correlatives
 - i. Lipid profile, complete metabolic panel, complete blood count with differential (CBC with diff) and hemoglobin A1C
 - ii. Serum beta-hydroxybutyrate
 - iii. Fasting serum glucose and insulin
 - iv. Vital signs, body weight, waist circumference
 - v. Platelet Mitochondrial Labs
 - iv. Performance Status
 - v. Quality of life (FACT-Br) survey (See Appendix 1)
 - vi. Neurocognitive testing (See Appendix VI)

[figure not shown]

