1. OBJECTIVES

- 1.1. Hypothesis/Rationale of the Study: Modified Atkins diet (MAD) concurrent with radiation therapy will produce ketosis and improve outcomes in patients with malignant gliomas due to increased sensitivity of the tumors to radiation therapy.
- 1.2. Primary Objectives
 - 1.2.1. Assessment of feasibility of inducing ketosis with MAD concurrent with radiation therapy by measuring serum beta-hydroxybuterate
 - 1.2.2. Assessment of fasting glucose and insulin levels with MAD concurrent with radiation therapy
 - 1.2.3. Assessment of compliance with MAD concurrent with radiation therapy
- 1.3. Secondary Objectives
 - 1.3.1. Assessment of 6-month progression-free survival in patients with high-grade gliomas with MAD concurrent with radiation therapy as compared to historical controls
 - 1.3.2. Safety of MAD concurrent with radiation and chemotherapy therapy
- 1.4. Exploratory Objectives
 - 1.4.1. Assessment of QOL changes with MAD concurrent with radiation therapy
 - 1.4.2. Assessment of cognitive function changes with MAD concurrent with radiation therapy
 - 1.4.3. Assessment of 2-year survival of patients with high-grade primary brain neoplasms with MAD concurrent with radiation therapy as compared to historical controls
 - 1.4.4. Assessment of mitochondrial respiration in peripheral platelets and correlate with cognitive findings

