10.2. Definitions

10.2.1. **Quality of Life (QOL)**: QOL will be assessed using the FACT-Br QOL tool. See Appendix I. QOL scores pre-intervention will be compared to post intervention-QOL score. QOL will also be obtained at the post-treatment visit #2 to assess if termination of intervention decreased QOL score. We understand that there are many variables that can affect QOL during this time other than the intervention.

10.2.2. **Two-year survival (2YS)**: Duration of survival will be defined as the number of months from diagnosis to death due to any cause.

10.2.3. **6-month progression free survival (6moPFS)**: will be defined as the percentage of patients without progression (defined below) at 6 months.

10.2.4. **Ketosis**: Will be defined as serum BHB ≥ 0.5 mM

10.2.5. **Compliance**: Dietary adherence is assessed by review of the daily food diary (Appendix II) serum ketone levels.

10.3. **Methods for Evaluation of Measurable Disease**: All baseline evaluations should be performed as closely as possible to the beginning of treatment. MRI imaging techniques that can be used to determine progression are:

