10.4.1.3. Clear progression of non-measurable disease

10.4.1.4. Any new lesion

10.5 Statistics

10.5.1 Ketosis will be defined as serum BHB > 0.05 mM throughout 6-week period of radiation and chemotherapy. We hope to find that in our given sample of 30 patients at least 50% will meet this criteria. We will compute a 95% confidence interval for this rate to estimate the likely range in the target population. A 10% increase in glutamate within the tumor on the post-RT MRI as compared to the pre-RT MRI will be considered evidence that the tumor is using ketones as fuel by the conversion to glutamate.

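### The primary ketosis rate has no baseline condition, so a patient already in ketosis before the diet who stays there is counted as an induction success

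*Combined protocol and SAP*

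**What the plan says.** The first primary objective (1.2.1) is "Assessment of feasibility of inducing ketosis with MAD concurrent with radiation therapy by measuring serum beta-hydroxybuterate". Section 3.1 makes this a single-arm study, and 3.3 sets its size: "Thirty evaluable patients will be enrolled".

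Section 4.2 begins "The presence of any of the following will exclude a patient from study enrollment" and lists items 4.2.1 to 4.2.8. Neither those items nor inclusion items 4.1.1 to 4.1.11 mention a current ketogenic or low-carbohydrate diet, or a BHB level at entry.

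Success is set out in 10.5.1: "Ketosis will be defined as serum BHB > 0.05 mM throughout 6-week period of radiation and chemotherapy". The target follows: "We hope to find that in our given sample of 30 patients at least 50% will meet this criteria". The analysis is "We will compute a 95% confidence interval for this rate to estimate the likely range in the target population". Section 10.2.4 gives another definition of ketosis, "Will be defined as serum BHB ≥ 0.5 mM", and 7.1 uses that same level. All of these are absolute levels; none refers to the patient's value before the diet.

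That value is collected. The schema and Appendix IV place a serum BHB at Pretreatment Visit 2 (day -28 to day -7), and 3.2 starts the diet about 7 days before chemoradiation. No section uses the Visit 2 BHB for eligibility or in the primary analysis.

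**The concern.** Inducing ketosis means moving a patient from not being in ketosis to being in it. The scored endpoint asks only whether BHB is above a level during treatment. The two agree for a patient who starts below the threshold. They differ for one who starts above it: that patient can show that ketosis was sustained through chemoradiation, but not that the study diet brought it about.

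With no control arm, the patient's own baseline is the only reference inside the study. Schema item 7.a, "RD will instruct patient on 3-day titration back to pre-study carbohydrate intake levels", suggests the authors expect pre-study intake to be higher than on the diet, but nothing makes that a condition of entry. I found no pre-treatment item that records usual carbohydrate intake, so the Visit 2 BHB is the only scheduled pre-diet marker of the problem.

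At stake is the only numerical feasibility target in the plan. An already-ketotic patient who stays in ketosis moves the rate towards that target, and the confidence interval, which reflects sampling error only, does not allow for it.

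**Working it through.** **Inputs.** n = 30 (3.3); target of at least 50%, i.e. 0.50 × 30 = 15 patients (10.5.1); 95% interval, method not stated (10.5.1). The number already in ketosis at Visit 2, k, is not in the documents and is varied here as an assumption.

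**The plan's own figure.** It states no power, null rate or interval limits, so there is nothing to reproduce beyond 15/30 = 50%. The 95% interval for 15/30 is 31.3% to 68.7% (exact), 33.2% to 66.8% (Wilson) or 32.1% to 67.9% (Wald). The exact half-width is (68.7 − 31.3)/2 = 18.7 points.

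**Step 1: direction.** Let p be the true success rate in patients who start below the threshold and s the rate in those who start at or above it. The all-patient rate is

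[k·s + (30 − k)·p]/30 = p + (k/30)(s − p).

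The bias is upward whenever s exceeds p, and is proportional to k. For example, with p = 0.40 and k = 3, s = 1 gives 0.40 + 0.10 × 0.60 = 0.46, and s = 0.80 gives 0.40 + 0.10 × 0.40 = 0.44.

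**Step 2: an observed 15/30 with the k patients removed.** Taking s = 1, the upper end, the rate in the others is (15 − k)/(30 − k).

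| k | Rate in the others | Exact 95% CI | Fall from 50% |
|---|---|---|---|
| 0 | 15/30 = 50.0% | 31.3–68.7% | 0 points |
| 1 | 14/29 = 48.3% | 29.4–67.5% | 1.7 |
| 2 | 13/28 = 46.4% | 27.5–66.1% | 3.6 |
| 3 | 12/27 = 44.4% | 25.5–64.7% | 5.6 |
| 5 | 10/25 = 40.0% | 21.1–61.3% | 10.0 |

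**Step 3: chance of reaching the target.** Take p = 0.40 (an assumption) and s = 1. The chance of at least 15/30 is P(X ≥ 15 − k) with X binomial(30 − k, 0.40): 17.5% at k=0, 23.4% at k=1, 30.5% at k=2, 38.7% at k=3 and 57.5% at k=5.

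**Step 4: who counts towards k.** The threshold is at least 0.5 mM in 10.2.4 and 7.1 but above 0.05 mM in 10.5.1, a ratio of 0.5/0.05 = 10. Anyone at or above the higher level also exceeds the lower one, so the 10.5.1 figure can only leave k unchanged or raise it. Until the sections agree, k is not defined.

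**The case against.** The strongest reply is that the problem may be empty. The documents give no sign that k is large, and at k=0 nothing changes. For k of 1 to 3 the shift of 1.7 to 5.6 points is well inside a half-width of about 19 points. The 50% is a hope with no test or go/no-go rule attached, and the needed BHB value is already collected. All of this stands and limits the size of the point. It does not remove it: the shift goes one way when s exceeds p, a confidence interval does not correct for bias, and a collected value helps only if the plan says how it will be used.

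A reader might infer several stronger things that the documents do not support:

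- *That the rate does not measure induction at all.* That would need a large k. Otherwise the rate is an overestimate in proportion to k.
- *That an already-ketotic patient is close to certain to succeed.* Section 10.5.1 requires ketosis throughout six weeks of chemoradiation. Steroids may be in use (4.1.9) and their dose may change (3.2.1), and 7.4 leaves diet compliance during an admission to the admitting physician and the patient. The value s = 1 is therefore an upper end.
- *That patients who start such a diet on their own are over-represented.* No section gives evidence on this.
- *That compliance is inflated against the 50% target.* That target belongs to ketosis only; 10.2.5 sets no target for compliance.
- *That baseline blood may follow the diet teaching because Visits 2 and 3 share a window.* The schema numbers the visits in order and has the labs confirmed at Visit 3. In any case the diet starts at about day -7, not at the teaching.

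**Conclusion.** The point holds in a limited form. The primary endpoint has no baseline condition, eligibility does not supply one, and the single-arm design offers no other reference. Any patient already in ketosis at Visit 2 who stays so is credited as induced.

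The size depends on k, which is unknown, and on s. With s = 1 and 15/30 observed, the rate among patients in whom ketosis could be induced is 46.4% at k=2, 44.4% at k=3 and 40.0% at k=5. With smaller s the overstatement is smaller; with k=0 there is none. This is a modest bias, worth removing because the correction uses data the study already has and should be fixed before results are seen.

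**What to change.** First reconcile the ketosis thresholds in 10.2.4, 7.1 and 10.5.1, since the agreed level decides both who succeeds and who was already ketotic.

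Then add to 10.5.1, for example: *The ketosis rate and its 95% confidence interval will be computed in all evaluable patients and also in those whose Pretreatment Visit 2 (pre-diet) BHB is below the ketosis threshold. The claim of induction and the comparison with 50% will rest on the second rate. Patients at or above the threshold at Visit 2 will be reported separately.*

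This needs no new sample and no change to eligibility. An exclusion criterion is not required: one framed around carbohydrate-restricted diets would need a definition of such diets and would also remove patients who are not in ketosis and do not bias the rate.

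The cost is a slightly smaller denominator and possibly a less favourable rate. In the cases above, the exact half-width goes from 18.7 points at k=0 to (66.1 − 27.5)/2 = 19.3 at k=2 and (61.3 − 21.1)/2 = 20.1 at k=5. If no patient is ketotic at Visit 2, the two rates coincide and nothing is lost.
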